5.4.3.2 Rituximab Administration (See 5.2)

5.4.3.3 Zevalin Administration

The Zevalin phase of the treatment program is a coordinate schedule of two rituximab doses, a single therapeutic Zevalin dose, and an imaging  In Zevalin dose (see sections 5.4.31. and 5.4.3.4). The therapeutic dose of Zevalin will be administered approximately one week after the first 250 mg/m^2 rituximab infusion (see 5.4.3.1 above), and following the second rituximab infusion.

Each patient will receive one therapeutic dose of ZEVALIN according to the dosing schema in Section 5.4.3.1, not to exceed 32 mCi of Y. Zevalin will be administered intravenously as a slow IV push over 10 minutes. Zevalin may be directly infused by stopping the flow from the IV bag and injecting the radiolabeled antibody directly into the infusion port. A **0.22 micron filter** must be on line between the syringe and the infusion port. (The 0.22 micron filter is not provided by IDEC Pharmaceuticals). Flush the line with at least 10 mLs of normal saline after ZEVALIN has been infused.

There is no provision for additional treatment courses for patients entered into this protocol.

# CAUTION WILL BE TAKEN IN THE HANDLING OF ALL RADIOACTIVE SAMPLES ACCORDING TO STANDARD PROCEDURES AND PRACTICES AT THE CLINICAL SITE.

#### ALL DOSES WILL BE CALCULATED USING ACTUAL BODY WEIGHT.

5.4.3.4 Indium-111 Imaging:

All patients will have imaging studies using In Zevalin antibody before the therapeutic course. The plan is as follows:

Day 1: A course of 250 mg/m^2 rituximab infusion, followed by 5.0 mCi of In Zevalin (for details please see Appendix I).

First whole body imaging: between 2-24 hours after infusion of In Zevalin and prior to urination (for details refer to Appendix I).

Second whole body imaging: 48-72 hours after the initial infusion of Indium.

Third whole body imaging: Only necessary if scan 2 showed a potential complication of biodistribution and would be used to make a treat or no treat decision.

5.4.3.5 Evaluations During the In Zevalin Imaging Period

During the imaging period, vital signs will be obtained every 15 minutes for the first hour during the Rituxan infusion, hourly during the remainder of the infusion, and immediately following the indium labeled Zevalin infusion. If vital signs are unstable, they will be monitored at 5-minute intervals until stable.

The purpose of the indium labeled imaging is two fold:

- To evaluate biodistribution of whole body gamma camera images
- To assess whether biodistribution is acceptable to proceed with 90Y Zevalin radioimmunotherapy.

The biodistribution of 111In Zevalin is to be determined from a visual evaluation of whole body gamma images during the first day (2-24 hours) and the second or third day (48-72 hours) after injection.

The expected biodistribution is as follows:

- Easily detectable uptake in the blood pool areas (including but not limited to the heart, major abdominal blood vessels, vascular areas of the head, lungs and pelvis) on the first day image, with less activity in the blood pool areas on the second or third day image.
- Moderately high to high uptake in normal liver and spleen during the first day and the second or third day images.
- Moderately low or very low uptake in normal kidneys, urinary bladder, and normal bowel on the first day image and the second or third day image.
- Tumor uptake may be visualized in soft tissue as areas of the increased intensity, and tumor bearing areas in normal organs may be seen as areas of increased or decreased intensity.

Altered biodistribution would be as follows:

- Diffuse uptake in normal lung more intense than the cardiac blood pool on the first day image, or more intense than the liver on the second or third day image.
- Kidneys with greater intensity than the liver on the posterior view of the second or third day image.

Biodistribution of 111In Zevalin should be assessed on the first day image and second or third day image. If desired, a third image can be obtained at 90 - 120 hrs to support the decision. If the patient has an altered biodistribution, the patient will be taken off study before proceeding to 90Y Zevalin radioimmunotherapy. (See Appendix I for additional details regarding data acquisition for 111In Zevalin).

5.4.4 Subsequent monitoring:

- For toxicity: see sections 7.7 (CBC, etc) and 7.6 (marrow cytogenetics), and Appendices A and L.
- For efficacy: see section 7.2 and 7.3

5.5 Maintenance Rituximab

5.5.1 Candidate patients: All responders (CR/CRu/PR), to start 6-8 weeks after Zevalin. 5.5.2 Schedule:

Rituximab: 375 mg/m^2 IV, a single dose every other month for 12 mo (6 doses total). Start 6-8 weeks after Zevalin, at approximately month 7.

NOTE: Rituximab maintenance can and should start on schedule, even if there is delayed hematologic recovery after Zevalin.

5.6. Chemotherapy Dose Modification Guidelines

5.6.1 Recommended Guidelines for Hematological Toxicity: for fludarabine and mitoxantrone (see 5.1.3):

Lowest granulocytes	Lowest Platelets	Modification		
>200	> 20,000	No change		
<200 for > 5 days and/or	< 20,000	Decrease one level		
documented infection with neutropenia	Bleeding	Decrease one level		

5.6.2 For all other toxicities (see Appendix B)

G	ra	de	
			-

- 0-2 No change
- 3 Decrease one level
- 4 Stop Treatment
- 5.6.3 Duration of therapy and intervals between courses:
- a) R-FND courses are recommended to repeated every 28 days, after verification of hematologic recovery.

b) Total length of R-FND treatment will be 4 courses for most patients. Exceptions should be discussed with PI, e.g. give more if response is slow (see sections 5.1.5 and 5.1.8), or stop early if there is evidence of cumulative myelosuppression, with more than 6 weeks before recovery of granulocytes to 1000 or more or platelets to 100,000 or more.

5.6.4 Patients older than 60 years will receive full doses of chemotherapy.

5.6.5 Anyone experiencing delayed recovery of granulocyte counts (>35 days) or neutropenic fever will be candidates for colony stimulating factor support, with the chemotherapy doses adjusted down one dose level.

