5.1 R-FND

5.1.1 Initial Dose Regimen of R-FND - Course 1: please note that there are 2 doses of rituximab for course 1 only:

AGENT	DOSE	DAY	ROUTE	TIME
Fludarabine	25 mg/m²/day	2-4	I.V.	5-30 minutes
Mitoxantrone	10 mg/m 	2	I.V.	5-30 minutes
Dexamethasone	20 mg/day	2-6	PO or I.V.	
Rituximab*	375 mg/m²/dose	1* & 8	I.V.	4-6 hours

\*For leukemic patients, because of the risk of lysis, rituximab Day 1 dose will be deferred to Day 3 (or later at clinician's discretion). Missed rituximab doses will be made up in subsequent courses; discuss with P.I.

Subsequent Monthly Dose Regimen of R-FND – Courses 2 and beyond: please note that there is only 1 dose of rituximab:

AGENT	DOSE	DAY	ROUTE	TIME
Fludarabine	25 mg/m²/day	1-3	I.V.	5-30 minutes
Mitoxantrone	10 mg/m 	1	I.V.	5-30 minutes
Dexamethasone	20 mg/day	1-5	PO or I.V.	
Rituximab	375 mg/m 	1	I.V.	4-6 hours

5.1.2 Rituximab is recommended to start two hours before fludarabine. Mitoxantrone is recommended to be given after the first dose of fludarabine. Courses are recommended to be repeated each four weeks, after documentation of recovery from the prior course, including platelets > 100,000, and granulocytes > 1500.

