5.1.3 Dose Levels

	-2	-1	0
Fludarabine	16 x 3	20 x 3	25 x 3
Mitoxantrone	6	8	10

Dose Reduction of rituximab is discouraged, but may be discussed with the P.I.

5.1.4 Patients are recommended to receive fludarabine phosphate I.V. over 5-30 minutes daily for 3 days. Mitoxantrone is recommended to be given I.V. over 5-30 minutes. Rituximab will be given as in section 5.1. Courses are recommended to be repeated every 4 weeks. Restaging on R-FND is recommended to be conducted after completion of 2 and 4 courses.

5.1.5 Patients achieving a stable partial response or demonstrating continued response after 4 courses may be given an additional 2 courses. Discuss with P.I.

5.1.6 Patients demonstrating progressive disease or no response after 2-4 courses will come off study. See section 9.1.

5.1.7 Dose adjustment to the next lower level will be made if pneumonia, septicemia, or other life-threatening infection occurs with any course. If recovery of the WBC or platelet count to the level prior to treatment exceeds 35 days, the dose may be decreased 1 level. If grade 3 or 4 toxicities to other organ systems develops, the dose level may be lowered 1 or 2 levels respectively.

5.1.8 Four courses is the intended limit for R-FND. For patients with substantial (>20%) ongoing shrinkage of measurable disease between courses 2 and 4 will receive additional R-FND, if their hematologic tolerance has been good. If such special circumstances warrant consideration of additional R-FND, please discuss with P.I.

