5.4 Zevalin Radioimmunotherapy (see Appendices I and J)

Candidate patients: PR or CR after R-FND x 4 5.4.1

5.4.2 Exclusions:

- persistent marrow infiltrate > 25% -- n.b., most such patients will not meet PR criteria anyway. ٠
- Hypocellular bone marrow (cellularity less than 15%) •
- Marked reduction in bone marrow precursors of one or more cell lines (granulocytic, megakaryocytic, erythroid)
- Platelet count <100.000/mm^3 ٠
- creatinine, bilirubin, AST/ALT or alkaline phosphatase > 2 x the upper limit of normal.
- Active infection
- pleural effusion

- G-CSF or GM-CSF within 2 weeks
- Performance status 3 or more

5.4.3 Schedule: Zevalin to start approximately 12-16 weeks after last course of R-FND, pending hematologic recovery as outlined above in 5.4.2

5.4.3.1 The Y isotope order form must be completed and faxed to the designated isotope vendor preceding the initial rituximab infusion. Patients will receive an initial infusion of 250 mg/m^2 rituximab. One week later, patients must receive a second infusion of 250 mg/m^2 of rituximab and 0.3 mCi/kg of ZEVALIN. The exact dose of ZEVALIN will be based on the patient's weight during the baseline evaluation. The maximum dose is not to exceed 32 mCi of Y.

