6.7.3 Recommended: PET scan

6.8 Any additional appropriate radiologic and radioisotopic examinations should be performed as indicated. **7.0 Evaluation During Study (see Appendix E)**  7.1 Recommended: Patients are recommended to be followed with CBC, platelet count and differential weekly for the first course, and q 2 wk thereafter. An SMA is recommended every month during chemotherapy.

7.2 After two courses, after four courses, 6-8 weeks after Zevalin, (i.e. approximately month 8 and 9), and 3 months later (approximately month 11-12), a full re-evaluation is to be performed, including:

7.2.1 Mandatory: CBC, differential, and platelet count, SMA-12, bone marrow aspiration and biopsy, CT scan of abdomen and pelvis, chest x-ray, and any other studies that were positive at baseline, such as CT head and neck or CT chest.

7.2.2 Optional: quantitative immunoglobulins. Surface marker studies on peripheral blood and bone marrow.

7.2.3 Prior to Zevalin therapy:

- CBC, chemistries, marrow, CXR; and
- Optional: Serum rituximab level

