7.9.3 Protocol required evaluations outside MDACC will be documented by telephone, fax or e-mail. Fax and/or e-mail will be dated and signed by the MDACC physician, indicating that they have reviewed it.

7.9.4 Changes in drug dose and/or schedule must be discussed with and approved by the MDACC physician investigator, or their representative prior to initiation, and will be documented in the patient record.

7.9.5 A copy of the informed consent, protocol abstract, treatment schema and evaluation during treatment will be provided to the local physician.

7.9.6 Documentation to be provided by the local physician will include drug administration records, progress notes, reports of protocol required laboratory and diagnositic studies and documentation of hospitalizations.

7.9.7 The home physician will be requested to report to the MDACC physician investigator all life threatening events within 24 hours of documented occurrence.

7.9.8 Patients will return to MDACC at least every 2-3 cycles for evaluation.

7.9.9 Physician to physician communication regarding protocol enrollment is required prior to the patient returning to the home physician and documentation of these conversations must be documented in the patient record.

7.9.10 A letter to the home physician outlining the patient's participation and requesting the home physician agreement to supervise the patient's care. The letter will be approved by the IRB as part of the protocol and a copy will be provided to the patient. (a copy of this letter can be found in Appendix M, and a copy of the chemotherapy instructions will also be sent to the outside physician (Appendix N).

7.9.11 The following documents are to be provided to the outside physician:

- a copy of the informed consent
- the protocol abstract

- the protocol treatment schema

- the protocol "Evaluation During Treatment" section

7.9.12 Communication of protocol required evaluations to MDACC investigators can be by telephone (dictation documentation required), fax, or e-mail. Authentication of fax and/or e-mail documents requires date and physician signature. This becomes part of the source documentation in the medical record.

7.9.13 The informed consent will describe the outside physician participation.

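### For grade 4 non-haematologic toxicity on R-FND, Section 5.6.2 says to stop, while Section 5.1.7 permits continuing two dose levels lower; the protocol body does not say which governs

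*Combined protocol and SAP*

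**What the plan says.** Section 5.6 of the protocol gives guidelines for modifying chemotherapy doses. Section 5.6.1 covers haematologic toxicity for fludarabine and mitoxantrone. Section 5.6.2 then takes everything else ("For all other toxicities (see Appendix B"): no change for grades 0 to 2, one level down for grade 3, and for grade 4 "4 Stop Treatment".

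Section 5.1.7, in the R-FND treatment section, covers the same ground: "If grade 3 or 4 toxicities to other organ systems develops, the dose level may be lowered 1 or 2 levels respectively". The levels are in 5.1.3. Level 0 is fludarabine 25 x 3 and mitoxantrone 10, level -1 is 20 x 3 and 8, and level -2 is 16 x 3 and 6 (mg/m²).

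For patients treated by outside physicians, 7.9.4 says that changes in dose or schedule "must be discussed with and approved by the MDACC physician investigator" or a representative before they are made.

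**The concern.** The two sections address the same patient: someone on R-FND with a severe toxicity outside the blood counts. One ends the chemotherapy and the other leaves room for more of the same drugs at a lower dose. A physician who reads only 5.1.7 could re-expose a patient after a grade 4 organ toxicity and believe the protocol allows it. A physician who reads only 5.6.2 would not. At stake are patient safety and consistent dosing across at most 50 patients, some of whom will be treated partly away from the centre.

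**Working it through.** **Side by side, by grade (non-haematologic toxicity)**

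| Grade | 5.1.7 | 5.6.2 | Agree? |
|---|---|---|---|
| 3 | may go down one level | go down one level | yes, in size |
| 4 | may go down two levels, R-FND continues | stop | no |

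The match at grade 3 suggests that both were written for the same situation. Life-threatening infection has its own one-level rule in 5.1.7 and is left out of this comparison.

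**Search for a tie-breaker in the protocol body**

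- 5.6.1 refers to the level table in 5.1.3, not to 5.1.7. 5.6.2 refers only to Appendix B, which 8.3 identifies as the toxicity grading system.
- 5.6.3(b) sends exceptions to the principal investigator, but on the number of courses.
- 7.9.4 requires approval of a dose change but does not say which rule the approver applies.
- 9.4 lists unacceptable toxicity as a ground for removal, with no grade attached.
- 11.3 gives the study chairman the last word where opinions on response or toxicity differ. 11.4 requires serious toxicity to be reported to the chairman. Neither sets the dose that follows.

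None of these settles the grade 4 case.

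**How far apart the two rules are**

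Inputs: the 5.1.3 levels; four planned courses (5.1.8 and 5.6.3(b)). Assumptions: the patient is at level 0; the course in which the event occurs is given in full; the stop in 5.6.2 means R-FND.

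Dose per course in mg/m²:
- Fludarabine: 25 x 3 = 75 at level 0; 16 x 3 = 48 at level -2.
- Mitoxantrone: 10 at level 0; 6 at level -2.

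Planned totals: 4 x 75 = 300 and 4 x 10 = 40.

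For an event in course c:
- Two levels down: fludarabine 75c + 48(4 - c); mitoxantrone 10c + 6(4 - c).
- Stop: share of plan c/4 for both drugs.

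| Event in course | Fludarabine, reduced | Mitoxantrone, reduced | Either drug, stopped | Gap (points, F / M) |
|---|---|---|---|---|
| 1 | 75 + 144 = 219, 73% | 10 + 18 = 28, 70% | 25% | 48 / 45 |
| 2 | 150 + 96 = 246, 82% | 20 + 12 = 32, 80% | 50% | 32 / 30 |
| 3 | 225 + 48 = 273, 91% | 30 + 6 = 36, 90% | 75% | 16 / 15 |

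After an event in course 4 there is normally no further R-FND to reduce or stop. A patient already at level -1 or -2 has no full two-level reduction left. The table does not apply to either.

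**The case against.** The strongest reply is that 5.1.7 only permits. It says the dose may be lowered, whereas 5.6.2 gives an instruction, so a physician who stops complies with both. That stands. A reader might infer that the two sections cannot both be followed, or that two physicians acting differently would each be fully compliant; the text supports neither. The defect is narrower: 5.1.7 permits what 5.6.2 rules out. It remains a defect, because 5.6 is itself headed as guidelines and does not plainly override 5.1.7.

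A second reply is oversight. Dose changes need approval at the centre, the study chairman hears of serious toxicity at once, and unacceptable toxicity is a ground for removal. This lowers the risk of unsupervised, inconsistent dosing. It does not remove it, because the people exercising that oversight work from the same two rules.

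A third is that the answer may lie elsewhere. Section 5.0 points to Appendix D, and the chemotherapy instructions for outside physicians are Appendix N. Neither was available, so a precedence rule there cannot be excluded. The body text should still agree with itself.

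**Conclusion.** The point holds as an internal contradiction in a dosing safety rule, confined to grade 4 non-haematologic toxicity during R-FND. For a patient at level 0 with the event in courses 1 to 3, the choice of section moves the delivered share of planned fludarabine and mitoxantrone by 15 to 48 percentage points. The conflict exists whatever the event rate.

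Four wider readings are tempting and are not supported:

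- **How many patients are affected.** The documents give no rate of grade 4 non-haematologic toxicity on R-FND. Any probability that the trial meets the conflict would rest on a guess, and would have to leave out course 4 events and patients already below level 0.
- **Loss of Zevalin.** Because 5.4.1 reads "Candidate patients: PR or CR after R-FND x 4", a reader might infer that stopping early costs a responder the radioimmunotherapy. That is a separate question, which 5.6.3(b) also raises by allowing early stopping for myelosuppression. Some patients with grade 4 organ toxicity could be excluded under 5.4.2 whichever dosing rule applied.
- **A flaw in the granulocyte rule.** A reader might infer that the 5.6.1 trigger, "<200 for > 5 days and/or", cannot be documented with counts every two weeks from course 2. Sections 5.6.1 and 7.1 are both recommendations, and nothing prevents a repeat count after a low value.
- **Bias in the primary analysis.** No effect on time to progression is shown. Section 10.3 includes every patient who receives any chemotherapy.

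**What to change.** Replace the grade 3 or 4 sentence in 5.1.7 with: *For toxicity to other organ systems follow 5.6.2: grade 3, decrease one level; grade 4, stop R-FND.* The infection and count-recovery sentences in 5.1.7 stay as they are. Naming R-FND also makes clear what is being stopped. Check that Appendices D and N carry the same rule.

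The cost is one sentence, with no added procedures or visits. The downside is that the discretionary two-level reduction is lost. If the sponsor intends to keep it, amend the grade 4 line of 5.6.2 instead, so that only one rule remains. That is a clinical choice for the sponsor.

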# 6.0 Pretreatment evaluation (see Appendix E)

6.1 A complete history and physical, including documentation of performance status, all measurable disease, screening for active or prior hepatitis B, as well as signs and symptoms shall be necessary.

6.2 Laboratory studies:

6.2.1 Mandatory (within 30 days of study entry): CBC, differential, and platelet count, chemical survey. Women of child-bearing potential will have a pregnancy test (serum HCG).

6.2.2 Recommended: Beta-2 microglobulin, quantitative immunoglobulins, serum protein electrophoresis, and immunofixation if monoclonal peak is identified. Plasma for soluble CD20 if possible.

6.3 Bone marrow aspirate and biopsy (bilateral biopsy; unilateral aspirate).

6.3.1 Marrow cytogenetics recommended. For exceptions, discuss with PI.

6.4 PCR for bcl-2

6.4.1 Mandatory: Baseline blood and bone marrow aspirates will be obtained for bcl-2 PCR. Contact our research nurse to make these arrangements, at the same time that eligibility screening is done. Please make these contacts early, so that candidate patients can have these studies done in a timely and efficient manner.

6.4.2 Optional: Immunophenotyping and gene rearrangement studies (PCR studies for bcl-2 mbr and mcr; and JH for bcl-2 negative patients) also should be performed on lymph node tissue, whenever possible. For fresh tissue obtained here, please arrange, through our research nurse, to have the sample triaged appropriately.

For biopsies done outside, prior to referral here, please arrange, through our research nurse, to have this archival tissue analyzed by [name] [contact]).

For cases whose diagnosis is based on limited tissue sample (e.g., FNA), it is strongly encouraged to obtain more tissue. Please discuss such cases with the P.I., if it is felt that treatment plans need to proceed despite suboptimal diagnostic material.

6.5 Optional: Cell surface markers (CD5, CD20, CD4, CD8, SIg, Kappa, Lambda) on peripheral blood and bone marrow. It is encouraged but not required that cells or extracted DNA be stored for future PCR studies.

6.6 Chest x-ray

6.7 CT and other scans:

- 6.7.1 Mandatory: CT scans of the abdomen & pelvis, within 2 months
- 6.7.2 Optional: CT scans of the head & neck and/or chest, as clinically indicated

6.7.3 Recommended: PET scan

6.8 Any additional appropriate radiologic and radioisotopic examinations should be performed as indicated. **7.0 Evaluation During Study (see Appendix E)**  7.1 Recommended: Patients are recommended to be followed with CBC, platelet count and differential weekly for the first course, and q 2 wk thereafter. An SMA is recommended every month during chemotherapy.

7.2 After two courses, after four courses, 6-8 weeks after Zevalin, (i.e. approximately month 8 and 9), and 3 months later (approximately month 11-12), a full re-evaluation is to be performed, including:

7.2.1 Mandatory: CBC, differential, and platelet count, SMA-12, bone marrow aspiration and biopsy, CT scan of abdomen and pelvis, chest x-ray, and any other studies that were positive at baseline, such as CT head and neck or CT chest.

7.2.2 Optional: quantitative immunoglobulins. Surface marker studies on peripheral blood and bone marrow.

7.2.3 Prior to Zevalin therapy:

- CBC, chemistries, marrow, CXR; and
- Optional: Serum rituximab level

